6.6. Interim Analyses

No interim analysis is currently planned.

7.0. Data Safety Monitoring Plan (DSMP)

All clinical investigations (research protocols testing biomedical and/or behavioural intervention(s)) should include the Data and Safety Monitoring Plan (DSMP). The purpose of DSMP is to provide a framework for appropriate oversight and monitoring of the conduct of clinical trials to ensure the safety of participants and the validity and integrity of the data. It involves involvement of all investigators in periodic assessments of data quality and timeliness, participant recruitment, accrual and retention, participant risk versus benefit, performance of trial sites, and other factors that can affect study outcome.

7.1. Data Protection

All study data and records will be treated confidentially and used solely for research purposes; We will ensure that, only the researcher will have access to the collected data/information obtained from the participant's records. We will also make sure that the data that are gathered are saved and well encrypted under password to prevent unauthorized access. If the subject and parents or the subject's legal representative withdraws the previously given informed consent or refuses to consent to continue in the trial, or if the subject dies and no consent is available from a subject's legal representative, or if the subject is lost to follow up then the subject's data will be handled as follows:

- Data collected will be retained by Hunazine Biotech and entered into the database.
- Safety events will be reported to the department responsible for global product safety, Hunazine Biotech/regulatory authorities according to local/national requirements.
- If data is used, it will always be in accordance with local law and IRB/IEC procedures.

7.2. Reports and Publications

Information obtained during the conduct of this trial is considered confidential and can be used by Hunazine Biotech for regulatory purposes and for the general development of the trial product. All information supplied and obtained by Hunazine Biotech in connection with this trial shall remain the sole property of Hunazine Biotech and is to be considered confidential information. No confidential information shall be disclosed to others without prior written consent from Hunazine Biotech. Such information shall not be used except in the performance of this trial. The information obtained during this trial may be made available to other physicians who are conducting other clinical trials with the trial product, if deemed necessary by Hunazine Biotech. One principal Investigator will be appointed to review and sign the CTR (Signatory Investigator) on behalf of all participating Investigators. The signatory Investigator will be appointed based upon the criteria defined by the International Committee of Medical Journal Editors (ICMJE) for research publications. The protocol will be registered in a publicly accessible database such as clinicaltrials.gov, CTIS/EudraCT, WHO Pan African Clinical Trial Registry (PACTR), or other applicable registers. In addition, after study completion (i.e., LPLV) and finalization of the study report the results of this trial will be submitted for publication and posted in a publicly accessible database of clinical trial results.

Hunazine Biotech commits to communicating, and otherwise making available for public disclosure, results of trials regardless of outcome. Public disclosure includes publication of a paper in a scientific journal, abstract submission with a poster or oral presentation at a scientific meeting, or by other means.

Hunazine Biotech reserves the right to not release data until specified milestones, e.g. when the clinical trial report is available. This includes the right to not release interim results of clinical trials, because the release of such information can invalidate the results of the entire trial.

At the end of the trial, one or more manuscripts for publication will be prepared collaboratively between Investigator(s) and Hunazine Biotech. Hunazine Biotech reserves the right to postpone publication and/or communication for less than 60 days to protect intellectual property.

The results of this trial will be subject to public disclosure at external web sites according to international regulations, which is reflected in Hunazine Biotech Code of Conduct for Clinical Trial Disclosure.

In all cases, the trial results shall be reported in an objective, accurate, balanced, and complete manner, with a discussion of the strengths and limitations of the trial. Screen In the event of any disagreement about the content of any publication, both the Investigators' and Hunazine Biotech's opinions shall be fairly and sufficiently represented in the publication.

Hunazine Biotech maintains the right to be informed of any Investigator plans for publication and to review any scientific paper, presentation, communication or other information concerning the investigation described in this protocol. Any such communication must be submitted in writing to the Hunazine Biotech Trial Manager prior to submission for comments. Comments will be given within four weeks from receipt of the planned communication.

7.3. Authorship

Authorship of publications should be in accordance with guidelines from The International Committee of Medical Journal Editors' Uniform Requirements (sometimes referred to as the Vancouver Criteria). The Investigator(s) offered authorship will be asked to comment and approve the publication. No permission to publish will be granted to any clinical research organization involved in the trial described in this protocol.

8.0. Ethical Assurance for Protection of Human rights

Describe the justifications for conducting this research in human participants. If the study needs observations on sick individuals, provide sufficient reasons for using them. Indicate how participants' rights will be protected, and if there would be benefit or risk to each participants of the study. Discuss the ethical issues related to biomedical and social research for employing special procedures, such as invasive procedures in sick children, use of isotopes or any other hazardous materials, or social questionnaires relating to individual privacy. Discuss procedures safeguarding participants from injuries resulting from study procedures and/or interventions, whether physical, financial or social in nature. [Please see Guidelines]

8.1. Regulatory and Ethical Considerations

The trial will be conducted in compliance with ICH GCP, applicable regulatory requirements, and in accordance with the Declaration of Helsinki. The sponsor and investigator will comply with all applicable regulations. In addition, the investigator will follow national and institutional requirements including, but not limited to Investigational Medicinal Product (IMP), clinical research, Informed Consent Forms (ICF) and Institutional Review Board (IRB) regulations. The approval of the trial protocol will be obtained from Ethical Review Committee (ERC) of icddr,b and Directorate General of Drug Administration (DGDA), which is functioning under the Ministry of Health & Family Welfare, Government of the People's Republic of Bangladesh. The investigator will be aware that representatives from DGDA or ERC may wish to inspect if the trial is in compliance to the protocol and adhered to GCP and local regulatory requirement. They may also look at eCRFs and associated study records to check the accuracy and consistency of the data.

All subjects included in the trial will be treated according to the icddr,b SoC for the treatment of cholera (attached) in addition to either VR-AD-1005 (75 subjects) or placebo (75 subjects). Subjects assigned to the trial will be transferred to a treatment regimen anticipated to be better than or equal to the treatment they receive at the time they enter the trial. However, they will have to spend some extra time, as additional visits to the clinic are required and some of these tests performed during the trial are outside normal practice.

There is no information available today indicating any risks in connection with the use of VR- AD-1005 FDC as compared to other products from the same pharmaceutical category. Data available for individual API indicate low risk which is far outweighed by the benefits.

All subjects participating in the trial will be monitored closely by the site with frequent visits and telephone contacts. When the subjects' participation in the trial ends, the subjects will consult their Investigator to decide on the best available marketed treatment.

8.2. Committees

Prior to commencement of the trial the protocol, any protocol amendments, subject information/informed consent form, any other written information to be provided to the subject and parents/subject's legal representative, subject recruitment procedures (incl. advertisement), if any, IB, available safety information, information about payments and compensation available to subjects if not mentioned in the subject information, the Investigator's current curriculum vitae (CV) and/or other documentation evidencing qualifications, and other documents as required by the local Institutional Review Board/ Independent Ethics Committee (IRB/IEC) should be submitted. The submission letter should clearly identify the trial identification number, version, European Union Drug Regulating Authorities Clinical Trials (EudraCT) number, title and/or the date of the documents that have been submitted to the IRB/IEC. Written approval favorable opinion must be obtained from IRB/IEC prior to commencement of the trial. During the trial, the Investigator or sponsor, as applicable, must promptly report the following to the IRB/IEC, in accordance with local requirements: updates to IB, unexpected SAEs where a causal relationship cannot be ruled out, substantial protocol amendments to the protocol, non- substantial protocol amendments according to local requirements, deviations to the protocol implemented to eliminate immediate hazards to the subjects, new information that may affect adversely the safety of the subjects or the conduct of the trial (including new risk/benefit analysis in case it will have an impact on the planned follow-up of the subjects),

annually written summaries of the trial status, and other documents as required by the local IRB/IEC and Ethics Review Committee.

Substantial protocol amendments must not be implemented before approval/favorable opinion, unless necessary to eliminate immediate hazards to the subjects.

8.3. Informed Consent Process

All potential study participants will be informed on the purpose of the study, procedures, risks and benefits of participating in the study, participant's expectations, and the compensation plan for their participation. It will be ensured that all information collected will be stored under lock and key or on the researchers' computer under password to prevent unauthorized access and used only for the purpose for which the data was collected. We will guarantee data privacy and confidentiality of all data obtained by ensuring that personal identifiers collected from participant folders would not be used during the analysis in the study. The participants will be encouraged to ask questions about the study, have the questions answered and then be given time to decide if they would participate in the study. It will also be emphasized that participation is voluntary, and that the participant has the right to withdraw themselves from the study at any time without prejudice. An impartial witness will be present during the informed consent discussions with an illiterate participant. A person who can only write his/her name and cannot read or write in Bangla will be considered as illiterate for the study purposes. The Investigator must obtain voluntary, personally signed and dated informed consent from participants before any study-related procedure. The original, signed ICF must be kept in the site study file; one copy of the ICF will be given to the participant / parents.

Use of Animals

Describe if and the type and species of animals to be used in the study. Justify with reasons the use of particular animal species in the research and the compliance of the animal ethical guidelines for conducting the proposed procedures.

No animals will be used in this study.

Collaborative Arrangements

Describe if this study involves any scientific, administrative, fiscal, or programmatic arrangements with other national or international organizations or individuals. Indicate the nature and extent of collaboration and include a letter of agreement between the applicant or his/her organization and the collaborating organization.

Hunazine Biotech will serve as the sponsor of the study and will provide the Clinical Trial Material for the phase II study. Hunazine Biotech will be responsible for cGMP manufacture of the investigational product.

Facilities Available

Describe the availability of physical facilities at site of conduction of the study. If applicable, describe the use of Biosafety Level 2 and/or 3 laboratory facilities. For clinical and laboratory-based studies, indicate the provision of hospital and other types of adequate patient care and laboratory support services. Identify the laboratory facilities and major equipment that will be required for the study. For field studies, describe the field area including its size, population, and means of communications plus field management plans specifying gender considerations for community and for research team members.

- The trial will be conducted at icddr,b Dhaka Hospital. It has adequate facilities for the management of acutely ill patients, particularly those are suffering from diarrheal illnesses. The patients are used to manage in short stay unit of the hospital. Those who require hospital stay for >48 hours with comorbidities require admission in longer stay unit. Additionally, the hospital has a dedicated intensive care unit for the management of seriously ill patients, like those with septic shock.
- The Clinical Haematology and Microscopy Lab, the Clinical Biochemistry Lab, and the Clinical Microbiology and Immunology Lab under the Clinical and Diagnostic Services, Office of Executive Director support clinical research activities beside performing routine diagnosis. We have the facility for sample processing and storage. We have refrigerator (4°C) and deep freezer ((-20°C and - 80°C) and backup generator for 24 hours supply.

Literature Cited

Identify all cited references to published literature in the text by number in parentheses. List all cited references sequentially as they appear in the text. For unpublished references, provide complete information in the text and do not include them in the list of Literature Cited. There is no page limit for this section, however, exercise judgment in assessing the "standard" length.

1. Nutrition & Clinical Services Division, icddr,b. Treatment for Cholera and other Diarrheas. Published online June 24, 2018.

CFR	Code of Federal Regulations
CICC	Calcium-induced chloride channel
Cl ⁻	Chloride ion
CLIA	Clinical Laboratory Improvement Amendments
CMP	Clinical Monitoring Plan
COC	Certificate of Confidentiality
CONSORT	Consolidated Standards of Reporting Trials
CRF	Case Report Form
CRO	Contract Research Organization
CTC	Cholera Treatment Centres
CTx	cholera toxin
CV	Cardiovascular
DCC	Data Coordinating Center
DHHS	Department of Health and Human Services
DSMB	Data Safety Monitoring Board
DRE	Disease-Related Event
EC	Ethics Committee
eCRF	Electronic Case Report Forms
EM	Electron Microscopy
FDA	Food and Drug Administration
FDAAA	Food and Drug Administration Amendments Act of 2007
FDC	Fixed-Dose Combination
FFR	Federal Financial Report
GCP	Good Clinical Practice
GLP	Good Laboratory Practices
GMP	Good Manufacturing Practices
GRS	Generally Recognized as Safe
GI	Gastrointestinal
GWAS	Genome-Wide Association Studies
HIPAA	Health Insurance Portability and Accountability Act
IB	Investigator's Brochure
ICD	International Classification of Disease
ICH	International Conference on Harmonisation
ICMJE	International Committee of Medical Journal Editors
IDE	Investigational Device Exemption

IND	Investigational New Drug Application
IP	Investigational Product
IRB	Institutional Review Board
ISM	Independent Safety Monitor
ISO	International Organization for Standardization
ITT	Intention-To-Treat
Kg	Kilogram
LSMEANS	Least-squares Means
MedDRA	Medical Dictionary for Regulatory Activities
ml	Milliliter
MOP	Manual of Procedures
MQAE	N-[ethoxycarbonylmethyl]-6-methoxy-quinolinium bromide
MSDS	Material Safety Data Sheet
NDC	National Drug Code
Na+	Sodium ion
NCT	National Clinical Trial
NHE3	Sodium-hydrogen exchanger 3
NIH	National Institutes of Health
NIH IC	NIH Institute or Center
OHRP	Office for Human Research Protections
ORS	Oral Rehydration Salt
ORT	Oral Rehydration Therapy
PBS	Phosphate buffered saline
PI	Principal Investigator
QA	Quality Assurance
QC	Quality Control
RCT	Randomized Controlled Trial
RDT	Rapid Detection Test
SAE	Serious Adverse Event
SAP	Statistical Analysis Plan
SMC	Safety Monitoring Committee
SOA	Schedule of Activities
SOC	System Organ Class
SOP	Standard Operating Procedure
UP	Unanticipated Problem
US	United States
WT	Wild type
WHO	World Health Organization

Appendix I

Schedule of activities

Procedures	Screening Hour - 4	Day1 Hour 0:00	Day 1 Time +5:00 hr	Day 1 Time+1 0:00 hr	Day 1 Ho_Time +15:00 hr	Day 2 Hour 0:00	Day 2 Time +5:00 hr	Day 2 Time +10:00 hr	Day 2 Time +15:00 hr	Day 3 Hour 0:00	Day 3 Time +5:00 hr	Day 3 Time +10:00 hr	Day 3 Time +15:00 hr	End of treatment
Informed consent	X													
Demographics	X													
Medical history	X													
Pregnancy screening	X													
Randomization and dispensation of numbered IP	X													
Concomitant medication review	X	X				X				X				
Physical exam (including Height and weight)	X	X				X				X				X
Vital signs BP, pulse, temperature	X	X				X				X				X
Blood collection for CBC	X	X				X				X				X
Blood collection for BMP	X					X								X
Assessment of stool output	X	X	X	X	X	X	X	X	X	X	X	X	X	X
Assessment of vomiting	X	X	X	X	X	X	X	X	X	X	X	X	X	X
Assessment of rehydration	X	X	X	X	X	X	X	X	X	X	X	X	X	X
Assessment of dehydration	X	X	X	X	X	X	X	X	X	X	X	X	X	X
Assessment of IV fluid infused	X	X	X	X	X	X	X	X	X	X	X	X	X	X
Assessment of water intake	X	X	X	X	X	X	X	X	X	X	X	X	X	X
Assessment of ORS intake	X	X	X	X	X	X	X	X	X	X	X	X	X	X
Assessment of urine output	X	X	X	X	X	X	X	X	X	X	X	X	X	X

Collection of stool samples for V. Cholerae confirmation	X													X
Stool collection for electrolytes	X					X								X
Administer study intervention		X	X	X	X	X	X	X	X	X	X	X	X	
Initiate rehydration and/or antibiotics treatment		X	X	X	X	X	X	X	X	X	X	X	X	
Adverse Events		X	X	X	X	X	X	X	X	X	X	X	X	X
Complete Case Report Forms (CRFs)	X	X	X	X	X	X	X	X	X	X	X	X	X	X

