4.5. Trial Assessments and Procedures

4.5.1. Screening/Baseline Assessments and Procedures

- Medical history: All patients admitted with secretory diarrhea with severe dehydration will be offered to participate in the study.
- Informed consent. Severely ill patients unable to sign the consent form will be resuscitated according to the proper SOPs, until they are able to make an informed decision regarding the enrollment.
- Randomization and assignment to treatment Group. IP assignment.
- Concomitant medication review.
- Physical examination: height, body weight, temperature, thirst, HEENT (note and record signs of dehydration, such as sunken eyes), skin (note and record signs of dehydration, such loss of turgor), level of consciousness using AVPU (active, response on voice or pain, unconscious) criteria, vomiting.
- Hydration status should be assessed in each participant including assessment of IV fluids, oral ORS intake and oral water intake.
- Vital signs: body temperature, heart rate, respiratory rate, blood pressure (including orthostatic blood pressure measurement when possible), urine output.
- Blood collection (5 ml) for Complete Blood Count (CBC), Basic Metabolic Panel (BMP) including serum electrolytes and creatinine.
- Stool collection for *V. cholerae* RDT (dark field microscopy) and culture.
- Initiate Re-hydration and antibiotic treatment in accordance with the SOPs for cholera patients until recovery.
- Initiate IP administration as soon as participants can tolerate oral intake.

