of IP/placebo, physical examination will be performed and vital signs will be obtained for initial three hours followed by at least 8 hourly for the whole treatment period and also at the end of treatment. Assessment of hydration status, including dehydration, vomiting, urine output, water intake, ORS intake or IV fluid infusion will be performed throughout the treatment period. Concomitant medication review will also be performed at least once in a day. Blood testing for the re-evaluation of the patient will be done according to the clinical condition of the patient and once at the end of treatment. Beside giving study specific treatment, all patients will be provided standard care and treatments. Standard of care (SoC) for adult cholera patients having severe dehydration includes rehydration with IV cholera saline (100ml/kg over 3 hours) and Doxycycline 300 mg after initial hydration; SoC also includes replacement of ongoing purging with ORS (if no persistent vomiting or no high purging) or IV fluid (if there is persistent vomiting or high purging). Adverse events, including SAE will be closely monitored, and appropriate treatment will be provided; if needed, patients will be referred to specialized clinics or hospitals. Recovery from diarrhoea will be assessed continuously through stool output and frequency, and stool culture will be performed to confirm the absence of *V. cholerae*. Feeding with a normal diet will be continued /initiated based on clinical feasibility; feeding with a normal diet will be resumed when vomiting has stopped and patients are able to tolerate oral intake. Patients will be fed meals prepared and dispensed under hygienic conditions. Street food will be prohibited due to the high risk of bacterial contamination, which may hinder case management and also invalidate the results of this study. Patients will receive 2 to 3 cooked meals per day. Even after discharge, health and wellbeing of the participants will be followed up with weekly phone calls or home visits; it will be ascertained if they are experiencing any side effects of the treatment or any other AE or SAE.

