4.10.2. Permitted Concomitant Therapy

Concomitant therapy should be administered to all patients in accordance with the icddr,b guidelines on the treatment of cholera patients with acute diarrhea. Important steps are listed below (**Table 5**).

Table 5-Assessment of dehydration status ⁽¹⁰⁾

Assess	Condition*	Normal	Irritable/Less active*	Lethargic / Comatose*
	Eyes	Normal	Sunken	Sunken
	Tongue	Normal	Dry	Dry
	Thirst*	Normal	Thirsty (drinks eagerly)	Unable to drink*
	Skin pulse*	Normal	Goes back slowly*	Goes back very slowly*
	Radial pulse*	Normal	Reduced*	Uncountable or absent*

Diagnosis		No sign of dehydration	If at least 2 signs including one (*) sign is present, diagnose. Some Dehydration	If some dehydration plus one of the (*) signs are present, diagnose Severe Dehydration
Management		A	B	C

A. No sign of dehydration – ORS

- 50 ml ORS per kg body weight over 4-6 hrs *plus* ongoing losses
- Send patient to home with 4 packets of ORS
- Continue feeding, including breast milk for infants and young children on

B. Some dehydration – ORS

- 80 ml ORS per kg body weight over 4 – 6 hours *plus* ongoing losses
- Observe patients for 6 - 12 hours.
- Continue feeding, including breast milk for infants and young children on breastfeeding
- Reassess patients and dehydration status frequently - hourly.

In case of frequent vomiting (>3 times in 1 hour) or some dehydration persists ≥6 hours even after oral rehydration therapy: Treat with I/V fluid

C. Severe dehydration – I/V solution containing sodium, potassium, chloride and bicarbonate (e.g. Ringer's Lactate/ cholera saline)

Start I/V fluid immediately:

- 100 ml / kg Adult and Children > 1 year
30 ml / kg in first 1/2 hour
70 ml / kg in next 2.5 hours
- Encourage the patient to take ORS solution as soon as he/she is able to drink without vomiting.
- Antibiotic, if needed, after full rehydration.
- Zinc-20 mg/day for 10 days in children 6 months-5 yr old.

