Secondary Endpoint 1, assessment of hydration control. There are two measurable parameters to be assessed in the patient hydration. Parameter 1 is the number of unscheduled hydration episodes. The numbers will be derived from the individual rehydration records, and the number of patients receiving IV rehydration will be expressed in % and compared for control and study intervention group. Alternatively, total number of IV rehydration episodes can be expressed as means for control and study intervention group and analyzed using Student's t-test. Parameter 2 is the volume of the oral rehydration solution received during the course of interventional treatment. Total volume of rehydration solution (oral and IV where applicable) will be derived from the individual rehydration records, expressed in ml/kg of patient weight, and analyzed as means using unpaired Student's t-test. Analysis subgroups will include 1) total hydration received over the course of study after first administration of interventional medication, and 2) hydration received during first 12 hours and 3) hydration received during first 24 hours.

Secondary Endpoint 2. Assessment of duration of diarrhea. Total duration of diarrheal illness is an important parameter in the assessment of antidiarrheal treatment efficacy. Study intervention is expected to reduce the overall duration of the diarrhea. Duration of diarrhea is assessed from first administration of study intervention until the termination of diarrhea, which is defined as first formed stool, or no stool for 12 consecutive hours. Duration of diarrhea will be derived from individual stool charts. Kaplan-Meier survival curves will be built to compare duration of diarrhea between control and intervention groups.

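### Appendix I first marks the start of rehydration in the first-dose column, which conflicts with the immediate IV start in section 4.10.2; the plan also leaves a variable share of the initial 100 ml/kg in its fluid-volume and IV-duration measures

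*Combined protocol and SAP*

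**What the plan says.** **Start of rehydration**

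- Appendix I has a column "Screening Hour - 4" followed by twelve dosing columns from Day 1 Hour 0. The row "Initiate rehydration and/or antibiotics treatment" has no mark at Screening and one in each dosing column, the same pattern as the study-drug row. The row "Assessment of IV fluid infused" is marked at Screening and in every later column.
- Section 4.10.2, plan C (severe dehydration): "Start I/V fluid immediately".
- Section 4.2.3 makes severe dehydration on arrival an inclusion criterion.
- Section 4.5.1, under Screening/Baseline: "Initiate Re-hydration and antibiotic treatment in accordance with the SOPs for cholera patients until recovery". The same section has patients who are too ill to sign resuscitated before they decide on enrolment.
- Section 4.9 gives standard care as "rehydration with IV cholera saline (100ml/kg over 3 hours").

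**Start of study drug**

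- Section 4.3 places the first dose directly after consent and randomization.
- Section 4.4.4 waits until the patient can swallow.
- Section 4.5.1: "Initiate IP administration as soon as participants can tolerate oral intake".
- Appendix I puts it 4 h after the Screening column.

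**What is counted**

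- Section 6.3 (Parameter 2) analyses "total hydration received over the course of study after first administration of interventional medication", and also the first 12 h and first 24 h.
- Table 1 and section 6.0 measure IV duration over the whole treatment period and per 24 h, with no rule for the initial phase.
- Unscheduled IV episodes are limited to the maintenance phase.
- Stool collection for efficacy starts at the first dose (section 4.5.2).

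**The concern.** Sections 4.5.3 and 4.9 both send the reader to the schedule of activities, and 4.9 does so while describing how patient safety is assured. A schedule that marks the start of fluids only with the first dose disagrees with the protocol's own care section, in a population that is all severely dehydrated. Site staff should not have to guess which one governs.

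The same ordering decides what the fluid measures contain. The initial 100 ml/kg is set by body weight, not by the study drug. If it is finished before the first dose, it lies outside the section 6.3 windows. If it starts with the first dose, it lies inside. A patient dosed midway has part of it counted. The measured volume and IV time then depend partly on when the patient could swallow a capsule.

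**Working it through.** **1. The passages side by side**

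| Place | Start of rehydration |
|---|---|
| Appendix I, initiation row | Hour 0, with the first dose |
| Appendix I, IV-fluid row | Fluid already assessed at Screening |
| 4.10.2, plan C | Without delay in severe dehydration |
| 4.5.1 | Under Screening/Baseline, and before consent in patients too ill to sign |

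The firm conflict is between the first and third rows. Section 4.5.1 fits poorly with Appendix I but does not flatly contradict it, because its list covers Screening and Baseline together and also contains the start of study drug. The literal gap is Hour 0 minus Hour -4 = 4 h.

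**2. The plan's own power figure**

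Inputs from section 5.0: mean 280 g/kg, SD 156 g/kg, 33% reduction, two-sided alpha 5%.

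Difference = 0.33 × 280 = 92.4 g/kg. The noncentral t gives power 0.835 at 50 per arm and 0.950 at 75 per arm, close to the stated 0.82 and 0.94. The normal approximation, Φ(92.4 / (SD × √(2/n)) − 1.96), gives 0.842 and 0.952. It is used below.

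**3. Size of what moves in or out**

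The amount is up to 100 ml/kg and 3 h of IV time per patient. At an assumed 50 to 70 kg, 100 ml/kg is 5 to 7 L.

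**4. Added noise in total fluid volume**

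The documents give no mean or SD for fluid volume. The stool figures (280, 156, difference 92.4) serve as an assumed stand-in. Let p be the fraction of patients whose full initial volume falls inside the window. p is also an assumption, and the initial volume counted is taken as independent of other fluid.

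Added SD = 100 × √(p(1 − p)). Combined SD = √(156² + added SD²).

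| p | Added SD | Combined SD | Power, 50 per arm | Power, 75 per arm |
|---|---|---|---|---|
| 0 or 1 | 0 | 156 | 0.842 | 0.952 |
| 0.25 | 43.3 | 161.9 | 0.814 | 0.938 |
| 0.5 | 50 | 163.8 | 0.805 | 0.932 |

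All-or-none counting is the worst case for a given mean share; partial counting adds less. By the same formula, IV duration gains an SD of at most 3 × √0.25 = 1.5 h.

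**5. Dilution**

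If the initial volume is outside for everyone, 92.4/280 = 33%. If it is inside for everyone, 92.4/(280 + 100) = 24%. The absolute difference is unchanged.

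**6. The 12 h window**

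The same volume enters a smaller total here. The documents give no SD; assume 60 to 100 ml/kg. At p = 0.5, √(60² + 50²) = 78 and √(100² + 50²) = 112. The required sample size rises by (78.1/60)² − 1 = 69% and (111.8/100)² − 1 = 25%. This range rests entirely on the assumed SD.

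**The case against.** A reader might infer that the plan makes severely dehydrated patients wait 4 hours for fluids. The documents do not support that. Appendix I itself records infused IV fluid, ORS intake and rehydration at Screening, so it presumes fluid may already be running. The row says initiate in all twelve dosing columns and joins rehydration with antibiotics, so it cannot be a literal single start time. Section 4.10.2 calls for an immediate start, section 4.5.1 provides resuscitation before consent, and sections 4.9 and 8.1 give every patient standard care. This makes the delay unlikely; it does not remove the mismatch in the table.

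A reader might also infer that the treatment comparison is biased or the primary result compromised. Neither follows. Allocation is randomized and blinded, so the noise should fall on both arms alike. The primary endpoint is stool output from the first dose. Hypothesis 2 is expressed through unscheduled rehydration episodes, whose IV definition already excludes the initial phase. Total volume is only Parameter 2 in section 6.3 and a listed comparison in section 6.1; it is not in the endpoint column of Table 1. Its window in section 6.3 is defined, so the fault is variable content, not a missing definition.

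Finally, 100 ml/kg of infused fluid and 92.4 g/kg of stool are different quantities. Setting one beside the other gives scale only.

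**Conclusion.** The conflict between the Appendix I row and section 4.10.2 plan C is plain on the page and should be resolved, because the schedule is an operative part of the protocol and every participant is severely dehydrated. The 4 h is the outer limit of a literal reading, not an expected delay. Which start time applies is for the clinical team.

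The analysis point is real but lesser. A variable share of up to 100 ml/kg and 3 h enters total volume, the 12 h and 24 h volumes and IV duration. For total volume the cost is about two points of power at 75 per arm (0.952 to 0.932) and a relative effect that could read as 24% instead of 33%. Both figures assume that the stool mean, SD and effect stand in for fluid, and the power figure takes the worst-case p of 0.5. The 12 h volume may be hit harder, but the documents give no figure to fix by how much. The effect is noise and dilution, not bias.

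**What to change.** 1. Reconcile the Appendix I row with sections 4.5.1, 4.9 and 4.10.2 so that all show one start time for rehydration, as decided by the clinical team. Cost: one corrected table row.
2. Record on the CRF the start time, completion time and volume of the initial scheduled rehydration. Cost: one or two new fields, since fluid volumes are already charted continuously during treatment under section 4.5.2.
3. In section 6.3, and for IV duration in Table 1, keep the window anchored at the first dose. Report initial scheduled fluid separately from later fluid, and add an analysis that excludes the initial scheduled fluid in every patient. Cost: one extra analysis and a sentence or two of text.

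Replacing the window with one restricted to the maintenance phase is not recommended. That phase can begin after the first dose, and its start differs by patient. Ongoing losses are also replaced before then, so the restriction could discard fluid that the drug is meant to influence.
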